4.2 Study Design

A 2x2 factorial design will be used to test the separate and combined effects of two biobehavioral interventions: *Move* and *Mind*. A factorial design lets us examine the interactive effects of a multi-component intervention, in which the interactive effect of the combined intervention is greater than the sum of each of the intervention main effects.

In the 2x2 factorial design, participants are randomized to 1 of 4 combinations of the 2 interventions being tested: (1) *Move*, (2) *Mind*, (3) *MindMoves*, and (4) usual care control. *Move*^{51,92,153–155,164–166} is a lifestyle physical activity program originally designed for community-dwelling women, tested for feasibility in older women with CVD, and redesigned to meet their needs and preferences. *Move* includes a personal physical activity goal with self-monitoring and five group meetings over 24 weeks based on social cognitive theory. *Mind* is the 36-hour BrainHQ cognitive training program^{48,105,113,167,168} modified for delivery in a lifestyle-focused tablet form over 24 weeks.

Data collection appointments are conducted at baseline and post-intervention at 24 (D2), 48 (D3), and 72 weeks (D4). Participants can continue to self-monitor steps in *Move* and will have access to the BrainHQ program in *Mind* following the end of the 24-week intervention. This will allow us to explore if continued use of these commercially available products predicts memory change, and to predict individuals more likely to maintain the physical activity and cognitive training. The usual care control group was selected to provide a comparison with older women not receiving the *Move*, *Mind*, or the combined *MindMoves* intervention.

4.2.a Narrative Study Description and Protocol

A. Introduction

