Participants who are assigned to *MindMoves* will complete both the *Move* and *Mind* interventions simultaneously for 24 weeks. The 24-week *MindMoves* combined intervention will consist of: (1) 5 group meetings focusing on motivation and barriers to increasing physical activity, (2) physical activity goal with Fitbit monitoring, and (3) 30-minute home-based BrainHQ cognitive training sessions on an iPad tablet 3 times per week. Interventionists will complete orientation for both *Move* and *Mind*. Participants will receive both a Fitbit and tablet to complete the combined intervention.

Participants in the usual care control group do not receive any *Mind*- or *Move*-related intervention. At the Center, providers assess and counsel patients regarding self-management and lifestyle habits at every appointment and offer the following resources (standard clinical practice for patients with CVD^{143,205}): (1) referral to a dietitian; (2) cardiac rehabilitation for patients with a new qualifying diagnosis;²⁰⁶ (3) referral to a gym for weight management for obese patients; and (4) educational materials on risk management. Resources are offered per any change in CVD risk status. Patients are excluded in the intervention group if currently in a physical activity program or cardiac rehabilitation. The usual care condition is necessary because we hypothesize that *Move* alone and *Mind* alone will improve memory performance and serum biomarkers more than usual care.²⁰⁷ We do not expect issues with attrition in this as prior physical activity studies with usual care groups have comparable drop-out rates across conditions.^{89,208} There are no physical activity or cognitive training clinical guidelines specifically for older adults with CVD.¹⁴³

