**NCT04556305**

**01.26.2021**

## STATISTICAL DESIGN AND POWER

### Power Analysis

**Power Analysis.** Power was estimated using design effect methods to account for clustering of cases within randomized cohorts. Due to the group meeting component of *Move*, participants will be randomized into groups of 10-11 participants. Assuming 24 cohorts of 10-11 participants each (6 cohorts per cell in the 2x2 factorial design; Figure 3), a 15% attrition rate (a conservative estimate based on our previous results), and a correlation of 0.7 between assessments of memory performance (as measured by neurocognitive tests), we estimate 80% power to detect an interaction effect ( $d = 0.30$ ) for significance ( $p < 0.05$ ) with  $N = 254$  participants (216 after accounting for attrition). This is a reasonable minimal effect size for the interaction effect described in Aim 1. Although existing systematic reviews suggest an estimated effect size of  $d = 0.50$ , we estimate  $d = 0.40$  given our previous work as a more conservative estimate for the main effects of the *Move* and *Mind* interventions. Assuming an effect size of  $d = 0.40$ , our study design has > 90% power. Thus, 254 women with CVD will be recruited (63-64 in each cell).

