### Statistical Analyses

Under the direction of [name], all analyses will use an intent-to-treat approach (i.e., participants analyzed according to their assigned cell; **Figure 3**) independent of their actual dose of each intervention. All analyses will employ multi-level mixed models with repeated observations (baseline, 24, 48, and 72 weeks) nested within participants, and participants nested within cohorts. Three parameters for factorial design will be included in the models: (1) *Move* main effect, (2) *Mind* main effect, and (3) *Move* x *Mind* interaction effect. Time and interactions of time with the factorial design parameters will be included in the models. Potential covariates in the multi-level mixed models are in Table 5. Although many of these covariates may relate to memory level, they are generally less likely to influence change over time. Covariates will be at Level 2 (person level) or Level 1 (assessment level) as appropriate. To minimize the number of covariates in the final models, we will first test each candidate covariate individually in models for each memory outcome change over time (time x covariate interaction). We will retain only significant covariates in the final models.

Time can be handled flexibly with multilevel mixed models, allowing us to model hypothesized patterns of change over time that deviate from linear or quadratic patterns. For example, we expect that *Mind* effects will be greatest from baseline to 24 weeks, followed by a change plateau; thus, a parameterization of time would reflect a relatively large increase from baseline to 24 weeks followed by stabilization after 24 weeks. Adding a term for this discontinuity in memory level (coded 0, 1, 1, 1 for baseline, 24, 48, and 72 weeks, respectively) allows us to test this pattern. In contrast, for the *Move* effects, we expect a more gradual linear change in memory from baseline through 48-72 weeks; therefore, a discontinuity term may not be needed. The general multilevel mixed model for the proposed analyses can be represented by the following equations:

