#### Cluster-Level Model

$$\beta_{00k} = \gamma_{000} + \gamma_{001}(\text{Move}) + \gamma_{002}(\text{Mind}) + \gamma_{003}(\text{MindMoves}) + \gamma_{004}(\text{ClinicSite}) + u_{00k}$$

$$\beta_{01k} = \gamma_{010}$$

⋮

$$\beta_{04k} = \gamma_{040}$$

$$\beta_{10k} = \gamma_{100} + \gamma_{101}(\text{Move}) + \gamma_{102}(\text{Mind}) + \gamma_{103}(\text{MindMoves}) + \gamma_{104}(\text{ClinicSite}) + u_{10k}$$

$$\beta_{11k} = \gamma_{110}$$

⋮

$$\beta_{14k} = \gamma_{140}$$

$$\beta_{P0k} = \gamma_{P00}$$

Where

$\gamma_{000}$  is grand mean (intercept) for the outcome measure;

$\gamma_{001}$  through  $\gamma_{003}$  are the intervention main effects and interaction effect on the mean for the outcome measure;

$\gamma_{004}$  is the Clinic Site effect on the mean for the outcome measure;

$\gamma_{010}$  through  $\gamma_{040}$  are the overall effects for the person-level covariates;

$\gamma_{100}$  is grand mean change over time on the outcome measure;

$\gamma_{101}$  through  $\gamma_{103}$  are the intervention main effects and interaction effect on change over time for the outcome measure;

$\gamma_{104}$  is the Clinic Site effect on change over time for the outcome measure;

$\gamma_{110}$  through  $\gamma_{140}$  are the overall effects for the person-level covariates on change over time of the outcome measure;

$u_{0jk}$  is the cluster-level random effect for the intercept; and

$u_{1jk}$  is the cluster-level random effect for the time slope.

It is expected that the person-level random effects for the intercept ( $r_{0jk}$ ) and time slope ( $r_{1jk}$ ) will be significant (i.e., there will be significant between-person variation in level of the outcome and rate of change over time). Although we will include them in the initial models, it is likely that the cluster-level random effects for the intercept ( $u_{0jk}$ ) and time slope ( $u_{1jk}$ ) will be non-significant. If non-significant, those random effects will be removed from the models. The time-varying covariates include time of day for the assessment (i.e., for models with BDNF as the dependent variable – see Aim 2 below) and discontinuities (see above).

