**Aim 1 (primary): To determine the independent and combined efficacy of Move and Mind interventions on memory performance among women  $\geq 65$  years with CVD. Hypotheses: Move and Mind each will improve performance-based memory (main effects). In addition, there will be an interactive effect such that MindMoves will provide greater memory benefit than the sum of the main effects of Move and Mind.**

Aim 1 tests the main effects of the individual interventions (i.e., Move and Mind) as well as the interaction between the interventions. Outcome measures will be collected at baseline and 24, 48, and 72 weeks post-baseline. Because we hypothesize intervention effects on memory outcomes over time, significant Move x Time, Mind x Time, and Move x Mind x Time effects will provide evidence of significant main effects and a

significant interaction effect, respectively (parameters  $\gamma_{101}$ ,  $\gamma_{101}$ , and  $\gamma_{103}$  above).

Measures for Aim 1 (see section 4.3):

Primary Measures for Aim 1:

- [1] East Boston Memory Test (episodic memory)
- [2] Category Fluency (semantic memory)
- [3] Digit Span Forwards and Backwards (working memory)

Secondary Measures for Aim 1:

- [4] NIH Toolbox® Fluid Cognition Index (episodic memory, working memory, executive function, processing speed)

***Aim 2 (secondary): To determine the independent and combined efficacy of the *Move* and *Mind* interventions on memory-related serum biomarkers (brain-derived neurotrophic factor [BDNF], vascular endothelial growth factor [VEGF], insulin-like growth factor 1 [IGF-1]) among women  $\geq 65$  years with CVD. Hypotheses: *Move* and *Mind* each will improve serum biomarkers (main effects). In addition, there will be an interactive effect such that *MindMoves* will show a greater increase in biomarkers than the sum of the main effects of *Move* and *Mind*.***

Aim 2 tests the effects of *Move* and *Mind* individually (main effects) and combined (interaction effect) on memory-related serum biomarkers (BDNF, VEGF, IGF-1) at 24, 48, and 72 weeks post-baseline. Analyses will use multi-level mixed models as described in Aim 1. Due to known variation in BDNF levels throughout the day, time of day of assessment will be included as a time-varying covariate for analyses of impact on BDNF.

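### The SAP never states the factorial coding, so its three parameters do not fix which of the alone, synergy and combined effects is tested, and its synergy hypothesis cannot hold under marginal main effects.

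*SAP*

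**What the plan says.** **Hypotheses.** SAP Aim 1 expects Move and Mind each to improve memory, labels these main effects, and adds that "MindMoves will provide greater memory benefit than the sum of the main effects of Move and Mind". Aim 2 repeats the pattern for the biomarkers. Protocol section 4.2 describes the same idea: "the interactive effect of the combined intervention is greater than the sum of each of the intervention main effects". The usual care paragraph of Protocol 4.2.a, part C4, justifies that arm differently: "we hypothesize that *Move* alone and *Mind* alone will improve memory performance and serum biomarkers more than usual care".

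**Model and tests.** SAP Statistical Analyses lists the factorial parameters as "1) *Move* main effect, (2) *Mind* main effect, and (3) *Move* x *Mind* interaction effect". The Cluster-Level Model writes the three regressors as Move, Mind and MindMoves, says that γ101 to γ103 "are the intervention main effects and interaction effect on change over time for the outcome measure", and calls γ100 a grand mean. No numerical coding is given. Aim 1 names three tests: Move x Time, Mind x Time and Move x Mind x Time. Its parameter list gives γ101 twice and omits γ102. Aim 2, which uses the Aim 1 models, ties the individual effects to the main effects and the combined effect to the interaction.

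**Power.** The SAP states 80% for an interaction of d = 0.30 with 216 analysed. For main effects of d = 0.40 it says "our study design has > 90% power".

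**The concern.** Four quantities are in play: the effect of each programme alone against usual care, the effect of each averaged over the other factor, the excess of the combination over the two alone effects (synergy), and the combination against usual care. The plan makes claims about all four but names three parameters, and the unstated coding decides what those measure.

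Two cases show what is at stake:

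- If neither programme works alone and only the combination does, marginal coding credits an effect to each programme, while 0/1 coding gives alone effects of zero.
- If the programmes are purely additive, the interaction is zero. A reader following Aim 2 would conclude that there is no combined effect, however large the benefit of MindMoves over usual care.

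**Working it through.** **1. The identity.** Let C, M, N and B be the mean changes under usual care, Move, Mind and MindMoves. Write a = M − C, b = N − C and S = (B − C) − a − b, where S is the synergy.

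- Marginal Move effect = ½[(M − C) + (B − N)] = a + S/2.
- Marginal Mind effect = ½[(N − C) + (B − M)] = b + S/2.
- Sum = a + b + S = B − C, whatever S is.

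Example: a = b = 0.4 and B − C = 1.4, so S = 0.6. The marginal effects are 0.7 + 0.7 = 1.4. The combination equals their sum despite a large synergy.

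**2. What each coding delivers (same example).**

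| Coding | γ101, γ102 | γ103 | Not a named parameter |
|---|---|---|---|
| 0/1 with product | a, b (0.4, 0.4) | S (0.6) | B − C |
| ±0.5 with product | a + S/2, b + S/2 (0.7, 0.7) | S (0.6) | a, b, B − C |
| ±1 with product | half the marginal effects (0.35, 0.35) | S/4 (0.15) | a, b, B − C |
| Cell indicators | a, b (0.4, 0.4) | B − C (1.4) | S |

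Every product coding tests S = 0 through γ103. None of the four gives a, b, S and B − C together.

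**3. Reproducing the stated power.** Inputs from SAP Power Analysis: N = 254, 15% attrition (254 × 0.85 = 215.9, so 216), 24 cohorts, 6 per cell, correlation 0.7. That gives 54 per cell and 216/24 = 9 per cohort. Assumptions: two-sided 0.05, normal approximation, one follow-up, and an ICC of 0 to 0.05, because none is stated.

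SE = c × sd × √(DEFF/216), with DEFF = 1 + 8 × ICC.

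- sd = √(2 × 0.3) = 0.775 for change, or √(1 − 0.49) = 0.714 adjusted for baseline.
- c = 2 for a marginal effect or the half-scale interaction S/2, √8 for an alone contrast (54 v 54), and 4 for the full S.

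For change at ICC 0, the half-scale SE is 2 × 0.775/√216 = 0.105. Then 0.30/0.105 − 1.96 = 0.89, which gives 81%.

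| Power (change / baseline-adjusted) | ICC 0 | ICC 0.02 | ICC 0.05 |
|---|---|---|---|
| Half-scale interaction, 0.30 | 81.2 / 87.0% | 75.3 / 81.8% | 67.2 / 74.2% |
| Marginal effect, 0.40 | 96.7 / 98.4% | 94.1 / 96.9% | 89.4 / 93.6% |
| Alone v usual care, 0.40 | 76.5 / 82.9% | 70.2 / 77.1% | 62.1 / 69.1% |
| Full excess S, 0.30 | 29.6 / 33.9% | 26.2 / 29.9% | 22.4 / 25.6% |

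The stated 80% is met exactly on the half scale at an ICC of about 0.004 (change) or 0.027 (baseline-adjusted). The full S would need to be 0.54 to 0.59 for 80% power even at ICC 0. A t reference with 20 df lowers the ICC 0 half-scale figures to 77.3% and 83.5%.

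**4. Sensitivity to the number of follow-ups.** Averaging three follow-ups gives sd = √((1 + 2 × 0.7)/3 − 0.49) = 0.557. The alone contrast then has 96.2%, 93.4% and 88.4% power at ICC 0, 0.02 and 0.05. But the half-scale interaction would have 97.7%, 95.7% and 91.7%, so the stated 80% would need an ICC of about 0.125. The full S at 0.30 still reaches only 50.8% at ICC 0.

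**5. The two cases in numbers.**

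- Synergy only: a = b = 0 and S/2 = 0.30. Each marginal effect is 0.30 with the same SE as the half-scale interaction, so the plan's own 80% is also the chance of declaring each main effect significant. Under 0/1 coding γ101 and γ102 are zero and are rejected about 5% of the time.
- Additive: a = b = 0.40 and S = 0. MindMoves minus usual care is 0.80 SD, and the interaction is zero.

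**The case against.** The best defence is that the SAP nowhere defines main effects as marginal averages. With ordinary 0/1 indicators and MindMoves as their product, γ101 and γ102 are the alone effects, γ103 is the excess over their sum, and the synergy sentence becomes a testable statement. This stands as far as it goes: the identity is a consequence of one reading, not of the documents as such. That reading is nevertheless the favoured one. The power figures reproduce only on marginal, half-scale contrasts, and a grand-mean γ100 fits centred coding better than 0/1, where it would be the usual-care slope (a label that can be used loosely). Choosing 0/1 would leave 0.30 as a full excess with far less than the stated 80% power.

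A reader might also infer three stronger things, which the documents do not support.

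- *Synergy cannot be tested.* It can: Move x Mind x Time tests non-additivity under any product coding. The fault is in the wording of the hypothesis.
- *The alone and combined hypotheses have no test at all.* All these contrasts are estimable from the planned model, some codings make some of them named parameters, and Aim 2 does give the combined effect a test, though of a different quantity. Under marginal coding the two main effects even sum to the combined effect. What is missing is a pre-specified contrast with its interval.
- *The plan implies an alone effect of only 0.40 − 0.30 = 0.10 SD.* The SAP offers 0.30 as a minimal interaction size and never assumes it jointly with 0.40.

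It is also fair that the sentence about Move alone and Mind alone serves to justify the usual care arm, and that the power above 90% is claimed only for main effects. It is still a stated hypothesis, and no named test is tied to it.

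**Conclusion.** The point holds as a fault of specification that should be fixed before analysis. It is not a flaw in the design or the data. The coding is unstated, so the meaning of the primary parameters is open. On the reading that the power section favours, the synergy hypothesis is worded so that it cannot be true, each main effect is the alone effect plus half the synergy, and combined efficacy is judged by a parameter that is zero under additivity even when the combination gains 0.80 SD.

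The algebra needs no assumptions. The power figures rest on an assumed ICC, a single follow-up, two-sided 0.05 and the normal approximation. On those terms an alone contrast at d = 0.40 has about 62% to 83% power, against the plan's figure of above 90% for main effects. If three follow-ups are averaged, the alone contrast can exceed 90% at a low ICC, but the plan's 80% for the interaction then no longer reproduces at that ICC.

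**What to change.** 1. State the numerical coding of Move, Mind and the third term, give that term one label, and correct the Aim 1 parameter list so that the Mind parameter is γ102.
2. In Protocol section 4.2 and SAP Aims 1 and 2, reword synergy as a benefit exceeding the sum of the Move-alone and Mind-alone effects, each against usual care.
3. Pre-specify three contrasts from the same fitted model, with confidence intervals: Move, Mind and MindMoves, each against usual care. Base claims about either programme alone on the first two and claims of combined efficacy on the third. Describe main effects as averages over the other factor.
4. State that the power above 90% applies to marginal main effects only. Give power for the alone contrasts at d = 0.40 with the assumed ICC: for 54 v 54 and one follow-up, about 77% to 83% at ICC 0, 70% to 77% at 0.02 and 62% to 69% at 0.05. Say that the 80% at d = 0.30 refers to the half-scale interaction; if 0.30 is the full excess, power is about 26% to 34% at ICC 0 to 0.02.

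The cost is wording in both documents and three extra estimates from a model already planned, with no new data. The downside is a less favourable power statement for the alone hypotheses and a few more reported contrasts.

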#### Person-Level Model

$$\pi_{0,jk} = \beta_{00k} + \beta_{01k}(\text{age}) + \beta_{02k}(\text{race}) + \beta_{03k}(\text{education}) + \beta_{04k}(\text{BMI}) + r_{0jk}$$

$$\pi_{1,jk} = \beta_{10k} + \beta_{11k}(\text{age}) + \beta_{12k}(\text{race}) + \beta_{13k}(\text{education}) + \beta_{14k}(\text{BMI}) + r_{1jk}$$

$$\pi_{P,jk} = \beta_{P0k}$$

Where

$\beta_{00k}$  is the outcome measure for cluster  $k$ ;

$\beta_{01k}$  through  $\beta_{04k}$  are the coefficients for person-level effects on the intercept;

$\beta_{11k}$  through  $\beta_{14k}$  are the coefficients for person-level effects on the time slope;

$\beta_{P0k}$  are the person-level means for the time-varying covariates;

$r_{0jk}$  is the person-level random effect for the intercept; and

$r_{1jk}$  is the person-level random effect for the time slope.

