Aim 3 examines depressive symptoms and genetic factors as potential moderators of intervention efficacy on memory performance and effect on memory-related serum biomarker levels. A continuous measure of baseline depressive symptomatology (CES-D) and dichotomous indicators of *BDNF* genotype and *APOE- $\epsilon 4$*  allele status will be added to the models in Aims 1 and 2. Intervention effect x time x moderator interaction effects will be evaluated for significant moderation of the intervention effects by these three variables. We expect that intervention effects will be attenuated by higher levels of depressive symptoms and by the presence of a *BDNF*Met genotype or *APOE- $\epsilon 4$*  allele. When significant moderation is found, we will test the extent to which moderation occurs between the intervention and uptake of the target behaviors (e.g., physical activity and cognitive activity) as well as between change in target behaviors and health outcomes (e.g., memory performance and memory-related serum biomarkers). For example, depressive symptoms are hypothesized to reduce the degree to which changes in physical activity and cognitive activity lead to improved memory. In addition, participants with higher levels of depressive symptoms may participate less in the intervention and therefore exhibit fewer changes in target behaviors. Though power is likely to be lower for Aim 3 than for Aims 1 and 2, these analyses will contribute important deductive data for planning future studies.

In terms of the multilevel model presented above, a person-level covariate ( $\beta_{15k}$ ) will be added to the time equation ( $\pi_{1jk}$ ). A corresponding cluster-level equation for  $\beta_{15k}$  also will be added to the equations. Parameters  $\gamma_{151}$ ,  $\gamma_{152}$ , and  $\gamma_{153}$  represent moderation of the *Move* main effect, *Mind* main effect and *MindMoves* interaction effect respectively.

$$\pi_{1jk} = \beta_{10k} + \beta_{11k}(\text{age}) + \beta_{12k}(\text{race}) + \beta_{13k}(\text{education}) + \beta_{14k}(\text{BMI}) + \beta_{15k}(\text{moderator}) + r_{1jk}$$
$$\beta_{15k} = \gamma_{150} + \gamma_{151}(\text{Move}) + \gamma_{152}(\text{Mind}) + \gamma_{153}(\text{MindMoves})$$

Measures for Aim 3 (see section 4.3):

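### The printed Aim 3 model lets the moderator affect change but not baseline level, so part of any baseline difference appears as change in γ150 and in slopes by moderator level

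*SAP*

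**What the plan says.** The SAP's Aim 3 text uses three baseline moderators: "A continuous measure of baseline depressive symptomatology (CES-D) and dichotomous indicators of" BDNF genotype and APOE-ε4 status. It first says in general terms that these "will be added to the models in Aims 1 and 2". It then gives the algebra: a person-level covariate β15k "will be added to the time equation", and "A corresponding cluster-level equation for" β15k is added. The two printed lines are the amended π1jk and β15k = γ150 + γ151(Move) + γ152(Mind) + γ153(MindMoves). No amended π0jk and no β05k are shown.

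The tests are stated as: "Intervention effect x time x moderator interaction effects will be evaluated for significant moderation of the intervention effects by these three variables". Only γ151, γ152 and γ153 are named as moderation. γ150 is in the model but is not named as a test.

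In the Person-Level Model, the same four covariates (age, race, education, BMI) appear twice. β01k to β04k "are the coefficients for person-level effects on the intercept", and β11k to β14k "are the coefficients for person-level effects on the time slope". Baseline is one of the four modelled observations, and r0jk "is the person-level random effect for the intercept".

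**The concern.** The printed model contains moderator × time and arm × moderator × time, but no effect of the moderator on level. It therefore forces women with different genotypes or CES-D scores to share one expected baseline, given the other covariates. The Statistical Analyses section itself expects candidate covariates to bear on memory level more than on change, so the term left out is the one more likely to be non-zero.

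A real baseline difference then has to go elsewhere. The random intercept takes up most of it and the moderator-by-time coefficient takes up the rest. Carriers who merely start lower would seem to decline faster. Explaining a significant three-way term normally means showing slopes for carriers and non-carriers within arm, and every such slope for carriers contains γ150.

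**Working it through.** **The plan's own figures.** The SAP gives no number for Aim 3. Its sample size reproduces: 254 × 0.85 = 215.9, so 216 after attrition, or 54 per cell.

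**Inputs from the SAP.** Four visits, coded t = 0, 1, 2, 3; correlation 0.7 between assessments; 216 women; α = 0.05 (two-sided assumed).

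**Assumptions not in the documents.** Total variance 1, split into random intercept 0.70 and residual σ² = 0.30 to match the correlation; linear time; no cohort variance; random-slope variance 0 or 0.01 per visit²; binary moderator with prevalence p = 0.25 or 0.5; baseline difference a = 0.3 or 0.5 SD; no true moderator effect on change.

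**Leak per visit.** Let V be the covariance matrix of one woman's four observations. With the moderator in the slope only, generalised least squares gives

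bias(γ150) = a × f, where f = (t′V⁻¹1)/(t′V⁻¹t).

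Under compound symmetry with intercept variance τ, put c = τ/(σ² + 4τ). Since Σt = 6 and Σt² = 14,

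f = 6(1 − 4c)/(14 − 36c).

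- τ = 0.70: c = 0.7/3.1 = 0.2258, so f = 0.581/5.871 = 0.099.
- The fitted random intercept also absorbs the omitted level effect, so τ = 0.70 + a²p(1 − p). For a = 0.5 and p = 0.25, τ = 0.747, c = 0.2272 and f = 0.547/5.821 = 0.094.
- Over all settings f is 0.093 to 0.099 per visit step. Over three steps this is about 28-30%. Adding the random slope does not change f.

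**False-positive rate.** SE(γ150) = 1/√{n p(1 − p) t′V⁻¹t}. Here n = 216 when γ150 is averaged over arms (effect coding), and n = 54 when it is the usual-care slope (0/1 coding). For a = 0.5, p = 0.25 and no random slope:

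- t′V⁻¹t = 5.821/0.3 = 19.40.
- n = 216: SE = 1/√(216 × 0.1875 × 19.40) = 0.036; z = 0.047/0.036 = 1.32; rejection 26%.
- n = 54: SE = 0.071; z = 0.66; rejection 10%.

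| Baseline difference | Bias per visit | Bias over 72 weeks | Rejection, effect coding | Rejection, 0/1 coding |
|---|---|---|---|---|
| -0.3 SD | -0.029 | -0.087 | 12-16% | 7-8% |
| -0.5 SD | -0.046 to -0.047 | -0.14 | 23-32% | 9-12% |

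The ranges cover both prevalences and both slope variances.

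**Simulation of the same model** (effect coding, 24 cohorts of 9, 2,000 runs per setting). With a binary moderator at prevalence 0.25 and a 0.3 SD deficit, mean γ150 was -0.087 to -0.093 SD over 72 weeks and was rejected 10-14% of the time. With CES-D at -0.2 SD per SD, it was -0.057 to -0.059 and was rejected 16-23% of the time. With an intercept term for the moderator, mean γ150 was within 0.006 of zero and was rejected 4-6% of the time.

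**The tested terms.** The leak a × f is the same in every arm when all arms have the same visit pattern, so it cancels from γ151 to γ153. In the simulation these stayed centred on zero with rejection of 4-6%, with or without the intercept term. The condition on follow-up matters because f depends on the visits observed. With only the first three visits, Σt = 3, Σt² = 5 and c = 0.7/2.4 = 0.2917, so f = 3(1 − 3c)/(5 − 9c) = 0.375/2.375 = 0.158.

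**The case against.** The strongest reply is that this does not touch what Aim 3 tests. Only γ151 to γ153 are named as moderation, and they are unbiased in expectation with balanced follow-up. The SAP neither tests γ150 nor says that it will report slopes by moderator level. That stands. A reader might infer that the Aim 3 moderation tests are invalid, or that false findings at 23-32% are built into the plan. The documents support neither. Those rates belong to a coefficient that is not a planned test, and they apply only if it is averaged over arms. The SAP does not state the arm coding.

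A second reply is that the intercept term may be intended. The general sentence about adding the moderators to the models could cover it, and the equations may only be showing where the tested parameters sit. Table 5, the list of candidate covariates, is not in the text available, so it cannot settle the matter. This is possible, but the explicit equations depart from the Person-Level Model's own pattern, and an analyst who codes them as printed would leave the term out.

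A reader might also infer that the follow-on analyses, linking change in behaviour to outcomes, are biased by the same omission. The SAP prints no equation for that step, so this cannot be shown. That step lacks the protection of randomisation whatever the intercept contains.

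**Conclusion.** The point holds as a limited defect in the printed model. About 9-10% of any baseline difference by moderator goes into γ150 per visit step, or about 27-30% over 72 weeks: roughly -0.09 SD for a 0.3 SD deficit and -0.14 SD for 0.5 SD. The harm is confined to γ150 and to slopes described by moderator level.

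The leak fraction rests on the SAP's correlation of 0.7, four visits, linear time and the assumed variance split. The absolute sizes also rest on baseline differences that the documents do not give; with no baseline difference there is no bias. Because Aim 3 is exploratory and its named tests are unaffected in expectation, this is a worthwhile correction and not a threat to the trial's conclusions.

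**What to change.** Add β05k(moderator) to the π0jk equation in the Aim 3 text, with the cluster-level equation β05k = γ050, and keep γ151 to γ153 as the tests. If the term is already intended, print it. Stating the arm coding would also make the meaning of γ150 clear.

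The cost is one line of SAP and code. The single term removes the bias and leaves the standard errors of γ151 to γ153 unchanged, because those are contrasts between arms and the added term is common to all arms.

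Arm × moderator terms on the intercept (γ051 to γ053) would mirror the slope equation and guard against chance baseline imbalance, but they are optional and not free. They reduce the slope information from 14 − 36c to 5, in units of 1/σ². For τ = 0.747 and no random slope, the standard errors of the tested terms rise by a factor √(5.821/5) = 1.08. Over the settings above the cost is about 7-8%, in an analysis for which the SAP already expects lower power.
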